4.6.1 Corticosteroid

Prior to randomization, oral CSs (prednisone or prednisone equivalent), may be used in accordance with the investigator's clinical judgment and best standard of care. See [APPENDIX 3](#) for examples of equivalents.

A maximum daily dose of 30 mg/day of oral CS will be acceptable for eligibility for the study, however, the daily dose must be tapered down to a maximum of 10 mg/day for at least 5 days prior to Day 0 (randomization day).

Tapering of steroids during the course of the study will be highly encouraged and should be evaluated at the protocol permitted visits (Day 0 through Day 60 and Day 120 through Day 150). Between Day 60 and Day 120, and between Day 150 and Day 210, oral CS doses must be held constant due to the endpoint evaluations occurring at Day 120 and Day 210.

- Once a patient has received the first dose of study drug (after Day 0), prednisone (or prednisone equivalent) dose is highly encouraged to continue tapering down as appropriate. The investigator should evaluate the prednisone dose at each visit and make the decision, within the protocol allowed windows.
 - Exception: Between Day 60 and Day 120, and between Day 150 and Day 210 (ie, within 60 days of primary and secondary endpoint assessments), oral CS doses must be held constant.

After Day 0 (first dose of study drug), a maximum of 1 oral CS “burst” for increased SLE disease activity will be allowed between Day 0 and Day 60, according to the following:

- The oral CS dose is allowed to increase to ≤ 40 mg/day of prednisone or equivalent, which must be tapered down to ≤ 10 mg/day within 2 weeks of initiation of the “burst”

- Alternatively, a single intramuscular (IM) dose of methylprednisolone (40 mg or equivalent) is permitted
- No increase of oral CS above baseline is permitted beyond Day 60

Treatment with inhalational CS therapy (eg, for asthma), or by any other route, but systemic administration, is allowed.

Treatment with intra-articular or intravenous CS is prohibited during the course of the study.

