5.5 Premature Discontinuation

While patients are encouraged to complete all study evaluations, they may withdraw from the study at any time and for any reason. Every effort will be made to determine why any patient withdraws from the study prematurely. If the patient is unreachable by telephone, a registered letter, at the minimum, should be sent to the patient requesting him/her to contact the clinic.

All patients who withdraw from the study with an ongoing AE or SAE must be followed until the end of study or until the event is resolved or deemed stable, respectively.

If a patient withdraws prematurely after dosing, an end of treatment (EOT) visit should be performed (Day 180) and a last follow-up visit 90 days after dosing should be scheduled (Day 270). Safety follow-up visit procedures based on the Schedule of Assessments (see [Section 5.4](#)).

Patient participation may be terminated prior to completing the study and the reason recorded as follows:

- AE/SAE
- Protocol deviation
- Lost to follow-up
- Patient withdraws consent at their own request
- Investigator decision
- Decision by sponsor (other than AE/SAE, protocol deviation, or lost to follow-up)

Withdrawn patients may be replaced after discussion between the investigator or designee and sponsor.

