8.1 Sample Size

Sample size in the Phase 1b part of the study is based on operational consideration.

The sample size in the Phase 2 portion is based on the primary endpoint, SRI-4 Response at Day 210. Approximately 156 additional patients will be randomized in a 2:1 ratio to BOS161721 versus placebo to achieve 132 evaluable patients in the FAS. This assumes

24 patients will drop prior to having received treatment and an evaluable post-baseline efficacy measure. Enrollment and randomization will be monitored in a blinded fashion and increased if needed to ensure at least 132 patients are randomized into the FAS.

A total of 132 patients randomized provides more than 80% power to detect a treatment difference of 25% in SRI-4 response rates at Day 210, based on a targeted 2-sided significance level of 10% and using a 2-sided Pearson's chi-squared test. This assumes of a response rate of 65% for BOS161721 and 40% for placebo, where missing data at Day 210 is carried forward from most recent non-missing result and patients are treated as a non-responder if a prohibited medication defined as a medication failure occurs.

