8.2 Statistical Methods

8.2.1 Analysis Populations

The primary efficacy analysis will be based on the FAS, defined as all patients who receive at least 1 dose of study treatment and at have least 1 evaluable post-baseline efficacy evaluation. FAS analyses will be conducted on the basis of the randomized treatment.

A per protocol (PP) analysis set may be defined to exclude major protocol violations from the efficacy analysis. The PP Population will include all patients from the FAS except those with major violations to the protocol deemed to impact the analysis of the primary endpoint. These violations will be identified based on blinded data prior to study unblinding. PP analyses will be conducted on the basis of the randomized treatment.

Safety analyses will be based on the safety analysis set (SS), defined as all patients who receive at least 1 dose of study treatment. Safety analyses will be conducted on the basis of actual treatment received.

Pharmacokinetic analysis will be conducted on the PK analysis set, defined as the FAS with sufficient concentration data for the calculation of PK parameters.

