8.2.3 Primary Efficacy Endpoint(s)

The proportion of patients who achieve a SRI-4 response at Day 210 will be assessed via Pearson's chi-squared analysis. The primary efficacy endpoint will be analyzed using the FAS and if needed repeated in the PP analysis set. Missing values will be addressed by employing a last observation carried forward (LOCF) analysis. Other imputation methods may be employed as a sensitivity analysis and will be described in the SAP. Additional analyses exploring impact of baseline factors such as baseline disease severity, race, and other characteristics may be performed.

Patients that received prohibited medications or unallowable CS usage as described in [Section 4.6](#) will be considered "medication failures" and will be treated as non-responders for the

primary efficacy analysis. The determination of medication failures will be reviewed using blinded data and finalized prior to unblinding.

The superiority of BOS161721 relative to placebo will be evaluated. If the proportion of SRI-4 responders for the selected POC dose in BOS161721 arm is higher than that of the placebo arm, then BOS161721 will be considered superior to placebo if the 2-sided p-value is less than 0.10. Secondary and exploratory endpoints for this POC portion will be evaluated based on the same statistical hypothesis.

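### With LOCF as the primary rule, an SRI-4 response last seen as early as Day 30 or 60 can be scored as a Day 210 response

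*Protocol*

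**What the plan says.** Under section 8.2.3 the Day 210 SRI-4 proportion "will be assessed via Pearson's chi-squared analysis" in the full analysis set (FAS). The missing-data rule is explicit: "Missing values will be addressed by employing a last observation carried forward (LOCF) analysis". Section 8.1 builds the same carry-forward into the planning rates. The only events turned into non-response are prohibited medication and unallowable corticosteroid use. Other imputation methods are optional sensitivity analyses left to the SAP.

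Section 8.2.1 makes the FAS the primary set, "defined as all patients who receive at least 1 dose of study treatment and at have least 1 evaluable post-baseline efficacy evaluation". In the Phase 2 schedule (Table 2), SLEDAI-2K, BILAG and PGA are first repeated at Day 30; the Day 15 visit has no efficacy assessment. Section 8.1 randomises 156 to obtain 132, on the basis that "24 patients will drop prior to having received treatment and an evaluable post-baseline efficacy measure".

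Section 4.6.1 permits one burst for increased disease activity between Day 0 and Day 60: "The oral CS dose is allowed to increase to ≤ 40 mg/day of prednisone or equivalent", to be tapered within two weeks. Section 5.5 asks a patient who withdraws after dosing for an end-of-treatment visit and a last follow-up visit 90 days after dosing. It does not ask for the scheduled visits to continue to Day 210.

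**The concern.** The endpoint is meant to describe disease state at Day 210. Under the stated rules it can instead record a state seen months earlier, in a patient who has since left. If patients on active drug leave while responding and placebo patients leave while not responding, carry-forward creates a difference between arms with no drug effect at Day 210.

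The FAS rule is a separate departure from analysing everyone treated. In Phase 2, randomisation is on Day -1 or the morning of Day 0 (Table 2 footnote), so few patients should be lost before dosing. Most of the 24 allowed for (24/156 = 15.4%) would then be dosed patients removed because of what happened after randomisation.

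**Working it through.** **Inputs from the protocol.** Section 8.1: "based on a targeted 2-sided significance level of 10% and using a 2-sided Pearson's chi-squared test"; "response rate of 65% for BOS161721 and 40% for placebo"; 2:1 allocation; 156 randomised (104:52), 132 in the FAS (88:44). The protocol gives no dropout rate after Day 30 and no carried-response rate, so those below are assumptions.

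**1. Route through the text.** Permitted burst or none, then SRI-4 met at Day 30 or 60, then withdrawal with no later assessment. No clause in 8.2.3 makes this patient a non-responder, and LOCF makes the patient a Day 210 responder. A patient who attends the visits in 5.5 may supply a later value, because the end-of-treatment and follow-up visits include SLEDAI-2K, BILAG and PGA.

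**2. The plan's own power.** Pooled rate (88 × 0.65 + 44 × 0.40)/132 = 0.567. Null SE = √[0.567 × 0.433 × (1/88 + 1/44)] = 0.0915. Alternative SE = √[0.65 × 0.35/88 + 0.40 × 0.60/44] = 0.0897. Power = Φ[(0.25 − 1.645 × 0.0915)/0.0897] = Φ(1.11) = 86.6%. Exact enumeration of the Pearson test gives 86.3%. The stated figure of more than 80% is correct.

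**3. False superiority with equal dropout but unequal carried response.** Assume 40% response among completers in both arms, dropout d per arm and carried response c. The analysed rate is 0.40(1 − d) + c·d. Results are exact, at 104:52:

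| d | c active / placebo | Analysed rates | P(declare superiority) |
|---|---|---|---|
| 0 | – | 40.0% / 40.0% | 4.9% |
| 15% | 40% / 20% | 0.34 + 0.06 = 40.0%; 0.34 + 0.03 = 37.0% | 9.7% |
| 15% | 50% / 15% | 0.34 + 0.075 = 41.5%; 0.34 + 0.0225 = 36.3% | 15.2% |

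For d from 10% to 20% the milder split gives 7.8% to 12.0%. The stronger split at d = 20% gives 20.7%.

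**4. False superiority with unequal dropout.** Assume true Day 210 response in 40% of each arm (missing counted as non-response) and that LOCF scores 30% to 50% of missing patients as responders. Exact, at 88:44:
- 15% missing in both arms: 4.8%.
- 20% active, 10% placebo: 9.0% to 13.1%.
- 10% active, 20% placebo: 1.4% to 2.3%.

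**5. How few carried responses matter.** At the planned result, 57/88 against 18/44, p = 0.009. With placebo unchanged, 50/88 gives p = 0.085 and 49/88 gives p = 0.110. Eight active responses carried forward but not present at Day 210 (57 − 49) would decide the test.

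**6. Power with missing counted as non-response.** Rates = planned rate × 132/156 × (1 − m), where m is the further fraction missing at Day 210 within the FAS, equal in both arms. Exact, at 104:52:

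| m | Active / placebo | Power |
|---|---|---|
| 0 | 55.0% / 33.8% | 81.1% |
| 5% | 52.3% / 32.2% | 77.7% |
| 10% | 49.5% / 30.5% | 74.1% |
| 15% | 46.8% / 28.8% | 70.4% |

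These figures keep all 156 in the denominator. Any of the 24 never dosed would leave it; if none of the 24 were dosed, the m = 0 case returns to 86.3%.

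**The case against.** The best defence has four parts.

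First, a reader might infer that every early leaver is scored from Day 30 or 60. The text does not support that. The visits required by 5.5 yield SRI-4 components, and if the last visit is counted from the last dose, as section 6.2.1.1 words it for pregnancy, a last dose at Day 120 puts it at Day 210. This stands. But 5.5 also labels that visit Day 270, which is too late to carry forward, and patients who attend neither visit remain exposed.

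Second, the burst route is narrow. A burst requires increased disease activity, SLEDAI-2K looks back 30 days and BILAG four weeks, and both arms may use it. It is possible under the text but cannot be sized, so the point does not rest on it.

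Third, a reader might infer that LOCF favours the drug. Step 4 shows it can go either way. Non-responder imputation is not neutral either: with 40% response among completers in both arms and 10% active against 20% placebo missing, the rates are 36% and 32%, and false superiority is 12.5% (exact, 104:52). This also stands, and is why the fix needs a further sensitivity analysis.

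Fourth, this is a proof-of-concept test at two-sided 0.10, the 24 are an enrolment allowance that can be topped up, and the SAP may add sensitivity analyses. That is fair, but optional analyses do not change the primary rule fixed here.

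**Conclusion.** The point holds. Section 8.2.3 lets an unobserved Day 210 response be counted from an earlier visit, and 8.2.1 removes some dosed patients from the comparison. Under the assumptions in step 3, false superiority at 15% dropout is about 10% to 15% against 4.9%. It is unchanged when missingness and carried response are alike in both arms, and below nominal when placebo loses more. The actual direction and size cannot be known from the protocol.

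Two further readings are not supported. The sample-size statement is not wrong: more than 80% reproduces under the stated rule. The unadjusted chi-squared test is not a defect either; adjusting for baseline SLEDAI-2K would be a matter of preference.

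**What to change.** 1. In 8.2.1 and 8.2.3, base the primary analysis on all randomised and dosed patients, with missing Day 210 SRI-4 counted as non-response. Keep LOCF as a sensitivity analysis and pre-specify one more, such as multiple imputation or a tipping-point analysis, because non-responder imputation is also sensitive to unequal dropout.
2. In 5.5, distinguish stopping study drug from leaving the study, and continue the scheduled efficacy assessments through Day 210 where the patient agrees. State how the last follow-up visit is timed.
3. In 8.1, restate power as a range: about 81% if total missing stays at 24 of 156, and about 78%, 74% and 70% with a further 5%, 10% and 15% missing at Day 210.

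The cost is a wording change plus follow-up visits for patients who stop drug. Stated power and the response rates in both arms will be lower. No extra patients are needed if that power is accepted. Holding 80% with a further 15% missing would take about 204 patients by the normal approximation: n on placebo = [(1.645 × 0.602 + 0.842 × 0.574)/0.180]² ≈ 67.1, rounded up to 68, and 3 × 68 = 204.

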2.2 Phase 2 Proof of Concept

OBJECTIVES	ENDPOINTS
Primary	

 To demonstrate a superior effect of BOS161721 at the chosen dose compared with placebo for response on the SRI-4 	Primary Efficacy Endpoint 
 The proportion of patients with a SRI-4 response at Day 210 (see Section 6.3.4.1)
Secondary	
To demonstrate a superior effect of BOS161721 at the chosen dose compared with placebo for response on clinical indicators of SLE activity, in adult patients with moderately to severely active SLE on limited background standard of care treatment	Secondary Efficacy Endpoints 
 The proportion of patients with: 
 SRI-4 response at each visit SRI-5 and SRI-6 response at each visit (Section 6.3.4.2) a sustained reduction of oral corticosteroid (CS) (≤ 10 mg/day and \leq Day 0 dose) between Day 120 and Day 210 new BILAG A flare or > 1 BILAG B flares relative to baseline through Day 210 PGA worsening a BICLA response a CLASI response medication failures Results and changes from baseline in: 
 CLASI swollen and tender joints ACR-28 SLEDAI-2K SLICC/ACR damage index Time to medication failure Duration of longest SRI-4 response Time to first SRI-4 response Time to BILAG A flare or > 1 BILAG B flare compared to baseline through Day 210
Safety	

 To assess safety and tolerability of repeat doses of BOS161721 at the chosen dose administered SC in adult patients with moderately to severely active SLE on limited background standard of care treatment 	Safety Endpoints 
 Incidence and severity of adverse events (AEs) and serious adverse events (SAEs), related AEs, AEs leading to study drug discontinuation, AEs by severity and relatedness Injection site reactions C-SSRS 12-lead ECGs parameter results at each visit and change from baseline Vital signs (blood pressure [BP], heart rate, and temperature) parameter results at each visit and change from baseline Clinical laboratory results and change from baseline Physical examinations changes from baseline ADAs Study drug exposure/compliance

Exploratory

• CCI [REDACTED]	
• CCI [REDACTED]

• CCI [REDACTED]	
• CCI [REDACTED]

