6.3.4.3 BICLA Response

The BICLA is a responder index developed to measure response to therapy, and it includes scores from the BILAG, SLEDAI-2K, and PGA. BICLA response is defined as 1) at least 1 gradation of improvement in baseline BILAG 2004 scores in all body systems with moderate disease activity at entry (eg, all B [moderate disease] scores falling to C [mild], or D [no activity]); 2) no new BILAG A or more than 1 new BILAG B scores; 3) no worsening of total SLEDAI-2K score from baseline; 4) $\leq 10\%$ deterioration in PGA score and 5) no treatment failure.⁴⁴ It is driven primarily by the BILAG, and has been used in Phase 2 and 3 mAb studies.⁴⁷

For the endpoints of BICLA response at Days 210, 240, and 270, patient scores will be completed and response determined.

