8 STATISTICS

The following analyses are planned:

- An IA will be performed during the last cohort of the MAD portion to determine dose selection for the POC part of the study.

- An additional analysis may be performed for the MAD portion of the study when all MAD patients have completed the safety follow-up or withdrawn from the study, and prior to final analysis. Data from the POC part of the study will be excluded from this additional analysis.
- The final analysis will be performed when all patients have completed the POC safety follow-up or withdrawn from the study.
- Safety analyses will be performed for DMC reviews throughout the study to evaluate dose escalation decisions and accumulating safety data. The frequency and details of the content and format of the safety review meetings will be described in the SAP and/or DMC charter.

All statistical analyses will be performed using Statistical Analysis Software (SAS®) Version 9 or higher.

The following standards will be applied for the analysis unless otherwise specified. Data will be summarized descriptively by treatment and overall for each study portion. For the MAD part of the study, BOS161721 will be summarized overall and by each dose level, and placebo patients from each cohort will be combined. Select parameters may be summarized using patients from both study parts. Statistical testing will be performed on data from the Phase 2 portion only.

Continuous data will be summarized using number, mean, standard deviation (SD), 25th and 75th percentiles, minimum, median, and maximum. Categorical data will be summarized by treatment group using frequency tables (number and percentage). Time to event data will be summarized using counts, medians, 25th and 75th percentiles, and standard error. All data will be listed for all patients.

Statistical inference will be based on a 2-tailed test with an overall 0.10 level of significance, unless stated otherwise.

The effects of noncompliance, background therapy use, treatment discontinuations, premature withdrawal from study and covariates will be assessed to determine the impact on the general applicability of results from this study. Exploratory analyses of the data will be conducted as deemed appropriate. Any deviations from the planned analyses will be described and justified in the final integrated CSR.

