8.2.4 Secondary Efficacy Endpoint(s)

Binary efficacy endpoints will be assessed via Pearson's chi-squared analysis. Continuous efficacy endpoints will be assessed via analysis of variance (ANOVA) or analysis of covariance (ANCOVA) and treatment will be compared using the F-test. Repeated measures mixed models may be performed to evaluate data collected at each visit and overall. Time-to-event endpoints will be assessed via Kaplan-Meier methodology and treatment will be compared using the log-rank test. The secondary efficacy endpoints will be analyzed on the FAS and if needed repeated in the PP analysis set. Details including handling of missing data and "medication failures" will be available in the SAP.

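### The p < 0.10 superiority rule is carried to every secondary and exploratory endpoint, so the stated overall 0.10 level holds only for the primary endpoint

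*Protocol*

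**What the plan says.** For the primary endpoint, Section 8.2.3 requires a higher SRI-4 response rate at Day 210 on active treatment; "then BOS161721 will be considered superior to placebo if the 2-sided p-value is less than 0.10". The next sentence extends this: "Secondary and exploratory endpoints for this POC portion will be evaluated based on the same statistical hypothesis".

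Section 8 sets the level for the whole plan: "Statistical inference will be based on a 2-tailed test with an overall 0.10 level of significance, unless stated otherwise".

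The secondary objective in Section 2.2 is worded as a claim: "To demonstrate a superior effect of BOS161721 at the chosen dose compared with placebo for response on clinical indicators of SLE activity". Its endpoints include "SRI-4 response at each visit" and "SRI-5 and SRI-6 response at each visit", further response proportions, changes from baseline, and time and duration endpoints. Section 6.3.4.3 adds visits for one of them: "For the endpoints of BICLA response at Days 210, 240, and 270, patient scores will be completed and response determined". Section 8.2.4 names the tests, for example "Binary efficacy endpoints will be assessed via Pearson's chi-squared analysis", with ANOVA or ANCOVA for continuous endpoints and the log-rank test for times to event.

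No order of testing, condition on the primary result or split of alpha is stated, and nothing calls the secondary p-values nominal. Section 8.3 says that type 1 error is not affected, but gives only the absence of an interim analysis in the POC part as the reason.

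**The concern.** A missing testing hierarchy would not be a fault in a protocol, because that is commonly left to the SAP. Here the protocol fixes a rule and describes it by a property that the rule lacks. If each secondary endpoint is judged for superiority at 2-sided p < 0.10, the level across them is not 0.10.

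What is at stake is the reporting of the secondary objective. If the trial missed SRI-4 at Day 210, a p-value below 0.10 on, say, SRI-5 at Day 60 could be presented as superiority under the protocol's own rule. A reader could take it as protected at an overall 10%. A proof-of-concept result guides further development, so the strength of such a statement matters.

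**Working it through.** **1. The plan's own figure.** Inputs from Section 8.1: 132 patients in the FAS at 2:1 (88 active, 44 placebo), 65% versus 40%, 2-sided alpha 0.10, Pearson chi-squared test.
- Pooled rate: (88 × 0.65 + 44 × 0.40)/132 = 74.8/132 = 0.567.
- Pooled standard error: √(0.567 × 0.433 × (1/88 + 1/44)) = 0.0915.
- Unpooled standard error: √(0.40 × 0.60/44 + 0.65 × 0.35/88) = 0.0897.
- Power: Φ((0.25 − 1.645 × 0.0915)/0.0897) = Φ(1.11) = 0.866. Exact binomial enumeration gives 0.863.

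The stated power of more than 80% is confirmed. With no effect, exact enumeration gives a drug-favouring primary result with probability 0.048 to 0.049 for common response rates of 30% to 50%. The primary rule behaves as intended.

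**2. Number of secondary tests.** Table 2 schedules SLEDAI-2K, BILAG-2004 and PGA at nine post-baseline visits (Days 30, 60, 90, 120, 150, 180, 210, 240 and 270).

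| Endpoint group (Section 2.2) | All visits | Through Day 210 |
|---|---|---|
| SRI-4 by visit, Day 210 excluded as primary | 8 | 6 |
| SRI-5 and SRI-6 by visit | 18 | 14 |
| BICLA response (Section 6.3.4.3) | 3 | 1 |
| Steroid reduction, BILAG flare, PGA worsening, CLASI response, medication failure | 5 | 5 |
| Changes in CLASI, swollen joints, tender joints, SLEDAI-2K, damage index | 5 | 5 |
| Time to medication failure, first SRI-4 response and BILAG flare; duration of longest SRI-4 response | 4 | 4 |
| **Total** | **43** | **35** |

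The protocol states no total. This count takes swollen and tender joints as two endpoints and each change at one visit. It leaves out the optional by-visit mixed models of Section 8.2.4 and the redacted exploratory endpoints, both of which would raise it.

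**3. Expected false results.** A 2-sided p < 0.10 in the drug's favour has probability 0.05 per test under no effect. The expected number does not depend on correlation: 35 × 0.05 = 1.75 and 43 × 0.05 = 2.15.

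**4. Chance of at least one.** For m tests whose normal test statistics share a common correlation ρ,

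P = 1 − ∫ φ(u) [Φ((1.645 − √ρ·u)/√(1 − ρ))]^m du.

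| Correlation (assumed) | m = 35 | m = 43 |
|---|---|---|
| 0 (independent, 1 − 0.95^m) | 0.83 | 0.89 |
| 0.3 | 0.56 | 0.60 |
| 0.5 | 0.42 | 0.45 |
| 0.7 | 0.29 | 0.31 |
| 0.9 | 0.15 | 0.16 |

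The SRI tests are nested and repeated over visits, so 43 tests were also simulated with a strongly correlated SRI block. Correlations decayed by 0.7 to 0.95 per visit and 0.8 to 0.95 per SRI level, with 0.3 to 0.7 among most other endpoints. The chance was 0.55 at the weakest setting and 0.28 at the strongest, which is close to the range in the table.

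**The case against.** The strongest reply has four parts.

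- **This is a phase 2 proof of concept, and the SAP may settle the matter.** Section 8 and Section 8.2.4 send further analysis details to the SAP, and both lists are introduced as examples. A reader might infer that the protocol leaves only missing data and medication failures to the SAP; the text does not say that. This part stands, so the absence of a hierarchy is not the point. The point is the wording that the protocol itself fixes.
- **The superiority verdict is written out only for SRI-4 at Day 210.** For the other endpoints the text speaks of the same hypothesis and does not repeat the threshold. That is literally true. But Section 8 supplies the 0.10 level for all inference and Section 2.2 supplies the aim of demonstrating superiority, so the plain reading is the same criterion for each.
- **Overall may mean only that alpha is not divided between interim looks.** Section 8.3 makes that reading possible, and the design has that property for the primary test. Section 8, however, applies the word to inference in general.
- **No success rule is tied to any single secondary test.** This stands. A reader might infer that one positive test meets the secondary objective, but the protocol says no such thing. A reader might also infer that the rule cannot tell an active drug from an inactive one. That does not follow, since a false-positive rate under no effect says nothing about how often a real effect would be detected.

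**Conclusion.** Wrong as written. The superiority criterion, carried to all secondary and exploratory endpoints, does not fit an overall 0.10 level. That level holds only for the primary endpoint.

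An ineffective drug would give about 1.8 to 2.2 false drug-favouring secondary results on average. The chance of at least one is roughly 0.3 to 0.6, against about 0.05 for the primary alone. This rests on the derived count of 35 to 43 tests and on assumed common correlations of 0.7 down to 0.3. A flat one-in-two figure would claim more than the protocol supports, because it gives no correlations. The direction does not depend on them: even at a correlation of 0.9 the chance is about three times that of a single test.

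The primary analysis is untouched in size and power.

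**What to change.** - **Sections 8.2.3 and 8:** state that the superiority criterion (2-sided p < 0.10) and the overall 0.10 level apply to the primary endpoint only. State that secondary and exploratory endpoints are reported as treatment differences with 90% confidence intervals and nominal p-values, with no conclusion of superiority.
- **Section 2.2:** reword the secondary objective so that it evaluates the effect and does not set out to demonstrate superiority.
- **SAP:** use the same terms, and settle the wording before unblinding.

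The cost is text only. No patients, visits or analyses are added, and primary power stays at 86%. The downside is that an isolated secondary p-value below 0.10 can no longer be called superiority.
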